9.2 Pharmacodynamics and immunogenicity

The immunological variable is the ADAb evaluated at scheduled visits up to 208 weeks in accordance with the schedule of assessments in [Table 2–1](#) and [Table 2–2](#).

ADAb will be assessed using a tiered approach: screening, confirmatory, and titer assays will be used.

Samples will first be evaluated in the screening assay using a false positivity rate of 5% (reported as ‘above the cut-point’ [ACP] or ‘below the cut-point’ [BCP]), followed by analysis of screened positive samples (reported as ACP) in the confirmatory assay (which is a drug depletion assay) to confirm the true positivity of the samples (reported as either ‘confirmed positive’ [CP] or ‘not confirmed positive’ [(NCP)]. Samples that are CP will be evaluated in a titration assay to quantify the ADA level and will be reported as titer (reciprocal dilution factor including minimum required dilution [MRD]). Screening, confirmatory and titer cut points of the respective assays will be determined by the bioanalytical laboratory which will report the bioanalytical result from the respective assays.

The following rule will be implemented for by-visit ADAb summaries where applicable:

- If the ADAb sample is collected within ± 21 days relative to the visit date at which the drug was administered (or ± 21 days from a scheduled visit at which dosing was not performed), the ADAb result for that sample will be associated with the scheduled visit and summarized accordingly. This will include unscheduled assessments as described in [Section 3.5](#) (if a dose was administered at an unscheduled visit). Samples collected outside this window will be excluded from the ADAb summaries and will be listed only.

The rule above will apply to by-visit summaries only; summaries of cumulative ADAb status and time to treatment-emergent positivity will use all available data. This rule will not apply for Visit 21 (Week 208), ET visit or the SFU visit as no dosing is planned at these time points. Thus, all ADAb data obtained at these visits will be included in the by-visit summaries.

ADAb status will be derived as follows:

- Sample that are either BCP or ACP and NCP will be defined as **ADAb negative**
- Sample values that are ACP and CP will be defined as **ADAb positive** (regardless of whether or not a titer is available)

In addition the ADAb status will be further classified on a subject level as outlined below:

- **Pre ADAb negative – treatment emergent ADAb negative (Category 1):**
 - Considering AS0009 data only (Category 1a): includes subjects who are negative at AS0008 Baseline and ADAb negative at all sampling points in AS0009 (including SFU).
 - Considering AS0008 and AS0009 data (Category 1b): includes subjects who are negative at AS0008 Baseline and ADAb negative at all sampling points in AS0008 and AS0009 (including AS0009 SFU).

- **Pre ADA_b negative – treatment emergent ADA_b positive (Category 2):**
 - Considering AS0009 data only (Category 2a): Includes subjects who are negative at AS0008 Baseline and ADA_b positive at any sampling point in AS0009 (up to and including SFU and including the AS0009 EV). This group also includes subjects who have a missing pre-treatment sample (either missing or insufficient volume) at AS0008 Baseline with one or more ADA_b positive samples in AS0009.
 - Considering AS0008 and AS0009 data (Category 2b): Includes subjects who are negative at AS0008 Baseline and ADA_b positive at any sampling point post treatment in AS0008 and/or AS0009 (up to and including AS0009 SFU). This group also includes subjects who have a missing pre-treatment sample (either missing or insufficient volume) at AS0008 Baseline with one or more ADA_b positive samples in AS0008 or AS0009.
- **Pre ADA_b positive – treatment emergent reduced ADA_b (Category 3):**
 - Considering AS0009 data only (Category 3a): Includes subjects who are positive at AS0008 Baseline, and ADA_b negative at all sampling points in AS0009 (including SFU).
 - Considering AS0008 and AS0009 data (Category 3b): Includes subjects who are positive at AS0008 Baseline, and ADA_b negative at all sampling points in AS0008 and AS0009 (including SFU).
- **Pre ADA_b positive – treatment emergent unaffected ADA_b positive (Category 4):**
 - Considering AS0009 data only (Category 4a): Includes subjects who are positive at AS0008 Baseline and are positive at any sampling point in AS0009 (including SFU) with titer values of the same magnitude as AS0008 Baseline (i.e. less than a predefined fold increase from the AS0008 Baseline value defined within the validation of the assay).
 - Considering AS0008 and AS0009 data (Category 4b): Includes subjects who are positive at AS0008 Baseline and are positive at any sampling point in AS0008 or AS0009 (including SFU) with titer values of the same magnitude as AS0008 Baseline (i.e. less than a predefined fold increase from the AS0008 Baseline value defined within the validation of the assay).
- For the purposes of this study, this is set at an increase of less than or equal to a 3-fold difference from AS0008 Baseline.
- **Pre ADA_b positive – treatment emergent ADA_b boosted positive (Category 5):**
 - Considering AS0009 data only (Category 5a): Includes subjects who are positive at AS0008 Baseline and are positive at any sampling point in AS0009 (including AS0009 EV and SFU) with increased titer values compared to AS0008 Baseline.
 - Considering AS0008 and AS0009 data (Category 5b): Includes subjects who are positive at AS0008 Baseline and are positive at any sampling point post treatment in AS0008 and/or AS0009 (including SFU) with increased titer values compared to AS0008 Baseline.

The increase in titer values is defined as an increase greater than a predefined fold increase from AS0008 Baseline value which is defined within the validation of the assay. For the purposes of this study, this is set at an increase greater than a 3-fold difference (ie, a minimum of a 4-fold increase).

The fold increase in ADAb is calculated as follows:

$$\text{Fold increase} = \left[\frac{\text{ADAb titer at time point} - \text{ADAb titer at AS0008 Baseline}}{\text{ADAb titer at AS0008 Baseline}} \right] \quad (14)$$

Note: For any subject who is positive at AS0008 Baseline and positive at a post-Baseline time point, but for whom titers are not available to determine treatment unaffected or treatment boosted status, the subject will be considered as treatment boosted (i.e., Category 5), assuming no other samples are available.

- **Inconclusive (Category 6):**

- Considering AS0009 data only (Category 6a): Includes subjects who have a positive pre-treatment sample at AS0008 Baseline and some AS0009 samples are missing, while other AS0009 samples are ADAb negative.
- Considering AS0008 and AS0009 data (Category 6b): Includes subjects who have a positive pre-treatment sample at AS0008 Baseline and some AS0008 or AS0009 samples are missing, while other AS0008 and AS0009 samples are all ADAb negative.

- **Total treatment-emergent (Category 7 [Categories 2 and 5 combined]):**

- Considering AS0009 data only (Category 8a): Includes subjects who are pre ADAb negative – treatment emergent ADAb positive (Category 2a) and pre ADAb positive – treatment boosted ADAb positive (Category 5a).
- Considering AS0008 and AS0009 data (Category 8b): Includes subjects who are pre ADAb negative – treatment emergent ADAb positive (Category 2b) and pre ADAb positive – treatment boosted ADAb positive (Category 5b).

- **Total pre ADAb positive (Category 8 [Categories 3, 4, 5 and 6 combined]):** Subjects that are tested ADAb positive at AS0008 Baseline.

- **Missing (Category 9):**

Considering AS0009 data only (Category 9a): Includes subjects who have a missing or negative pre-treatment sample at AS0008 Baseline and all AS0009 samples are either missing or ADAb negative.

- Considering AS0008 and AS0009 data (Category 9b): Includes subjects who have a missing or negative pre-treatment sample at AS0008 Baseline and all AS0008 or AS0009 samples are either missing or ADAb negative.

The following summaries, figures and listings will be produced:

- Summary tables displaying the number and percentage of subjects with a positive ADAb status at each AS0009 visit and at any visit by treatment group at completion of AS0008 and overall. Two tables will be presented:
 - Considering ADAb status in AS0009 only
 - Considering ADAb status in AS0008 and AS0009 (this table will include only the overall summary visits as detailed below).

For the overall summary at any visit two summaries will be presented as follows (all summaries exclude data obtained at AS0008 Baseline):

- AS0009 data only: Including any visit during the AS0009 treatment period (as defined in [Section 3.2.2](#)). Thus, this summary will exclude data obtained at the SFU visit and will include data obtained at the AS0009 EV.
- AS0009 data only: Including any visit during AS0009. Thus, this summary will include both data obtained at the SFU visit and at the AS0009 EV.
- AS0008 and AS0009 data: Including any visit during the AS0008 and AS0009 treatment period. Thus, this summary will exclude data obtained at the AS0009 SFU visit.
- AS0008 and AS0009 data: Including any visit during AS0008 and AS0009. Thus, this summary will include data obtained at the AS0009 SFU visit.
- Summary tables (by treatment at completion of AS0008 and overall) of the time point of the first occurrence of ADAb treatment-emergent positivity during AS0009, including the AS0009 EV and the SFU visit. This summary will include the following categories:
 - Category 2: Pre ADAb negative – treatment-emergent ADAb positive
 - Category 5: Pre ADAb positive – treatment-boosted ADAb positive

The table will summarize the number and percentage of subjects who are either treatment-emergent ADAb positive or treatment-boosted ADAb positive for the first time at the specified time point in AS0009 and will include the cumulative number and percentage of subjects with treatment-emergent ADAb positive results at each time point.

The table will be repeated considering ADAb status at each visit in both AS0008 and AS0009 and will therefore display all visits in both AS0008 and AS0009.

An additional table will be presented considering ADAb status at each visit in both AS0008 and AS0009, and will be presented by actual treatment at randomization in AS0008 only.

- Summary tables displaying the number and percentage of subjects in each of the ADAb categories as defined above by treatment at completion of AS0008. Two tables will be presented:
 - Considering data from AS0009 only
 - Considering data from AS0008 and AS0009
- The time to achieving treatment-emergent ADAb positivity, by treatment group at completion of AS0008 and overall (3 lines per plot), will be graphically presented. Subjects

will be considered to have an event at the time point at which treatment-emergent ADAb positivity is first achieved. This plot will display the cumulative percentage of subjects with treatment-emergent positivity and will include the following categories:

- Category 2: Pre ADAb negative – treatment-emergent ADAb positive
- Category 5: Pre ADAb positive – treatment-boosted ADAb positive
 - Category 2 and Category 5 subjects will be combined in 1 group (3 lines per plot) if the percentage of subjects in each treatment group in Category 5 is <10%.

The figure will be repeated considering data from both AS0008 and AS0009 and will therefore display all visits in both AS0008 and AS0009.

In the event that $\geq 10\%$ of subjects in either treatment group are classified as Category 5 the figure will be repeated by treatment at completion of AS0008 and overall and by ADAb status (6 lines per plot). This will be implemented for both plots (considering only AS0009 and considering data from both AS0008 and AS0009).

An additional figure will be presented considering data from both AS0008 and AS0009, and will be presented by actual treatment at randomization in AS0008 only. This figure will be presented as follows:

- If $<10\%$ of subjects in each treatment group (based on treatment at randomization) are classified as Category 5, the figure will be presented with 5 lines on 1 plot (1 for each treatment) and both categories combined
- If $\geq 10\%$ of subjects in any treatment group (based on treatment at randomization) are classified as Category 5, the figure will be presented by category and treatment at randomization with separate plots (each with 5 lines) for each category
- A summary of efficacy response (ASAS40 responders [based on NRI]) as a function of ADAb titer will be presented graphically. The x-axis will display the ADAb titer at the AS0009 Week 48 time point (categorized as negative, Q1, Q2, Q3 and Q4 where the latter represents the quartiles for the ADAb titers at Week 48) and the y-axis will display percentage of ASAS40 responders at the Week 48 time point within each titer category.

Subjects with negative ADAb results at the Week 48 time point will be included in the ‘negative’ category on the x-axis; subjects with missing ADAb data at the Week 48 time point will be excluded from the plot. The figure will be based on the FAS.

- A summary of efficacy response (ASAS40 responders) versus time will be presented graphically including the following ADAb groups (3 lines per plot):
 - ADAb positive
 - Defined as subjects having at least 2 ADAb positive samples during AS0009 (including AS0009 EV and excluding SFU) regardless of other ADAb negative samples and/or missing or inconclusive samples
 - ADAb negative

- Defined as subjects for whom either (1) all samples in AS0009 (including AS0009 EV and excluding SFU) are ADA_b negative and there are no missing or inconclusive samples or (2) only 1 sample in AS0009 is ADA_b positive and all other samples in AS0009 (including AS0009 EV and excluding SFU) are ADA_b negative or missing/inconclusive or (3) only 1 sample is missing/inconclusive and the remaining samples are ADA_b negative (excluding SFU).
- Missing
 - Defined as subjects who do not fulfil the criteria for one of the 2 groups listed above.

The figure will be repeated considering ADA_b status based on AS0008 and AS0009 combined, with the following definitions:

- ADA_b positive
 - Defined as subjects having at least 2 ADA_b positive samples during AS0008 and AS0009 (excluding AS0008 Baseline and AS0009 SFU and including AS0009 EV) regardless of other ADA_b negative samples and/or missing or inconclusive samples
- ADA_b negative
 - Defined as subjects for whom either (1) all samples in AS0008 and AS0009 are ADA_b negative and there are no missing or inconclusive samples or (2) only 1 sample in AS0008 or AS0009 is ADA_b positive and all other samples in AS0008 and AS0009 are ADA_b negative or missing/inconclusive or (3) only 1 sample is missing/inconclusive and the remaining samples in AS0008 and AS0009 are ADA_b negative. All 3 definitions exclude AS0008 Baseline and AS0009 SFU and include AS0009 EV.
- Missing
 - Defined as subjects who do not fulfil the criteria for one of the 2 groups listed above.

Both figures described above will be based on the FAS and the data for ASAS responders will be based on NRI. If the percentage of subjects in the missing category is $\leq 5\%$, this category will be omitted from the plot.

- Spaghetti plots of ADA_b titer (y-axis) by visit (x-axis), separated by treatment group at completion of AS0008 for all ADA_b positive subjects. This plot will include the following ADA_b categories, based on data collected in AS0009:
 - Category 2: Pre ADA_b negative – treatment-emergent ADA_b positive
 - Category 5: Pre ADA_b positive – treatment-boosted ADA_b positive

Separate plots will be presented for each treatment group with both categories on the same plot. Plots will be presented using a semi-logarithmic scale for the ADA_b titers (ADA_b negative samples will therefore be excluded from the plot). The x-axis will reflect time from the AS0009 EV.

- Listings of individual subject-level ADA_b results will be presented for the following:
 - Including only data from AS0009.

- Including data from both AS0008 and AS0009.

The listing of AS0009 data will also include flags for ADA_b measurements that were excluded from the by-visit summaries. The reason for exclusion will be one of the following:

- Dosing performed out of window
- Sample collected out of window relative to current or previous dose
- Sample collected out of window relative to previous dose (missed or no dose at current visit)
- More than one sample obtained at the same visit
- Sample collected out of window relative to current dose or visit date (applicable to ADA_b data only)

Any ADA_b measurements that were outside the tolerance limit of the assay will also be flagged in the listing.

All outputs described in this section will be presented using the SS, unless otherwise stated.

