9 PHARMACOKINETICS AND PHARMACODYNAMICS

9.1 Pharmacokinetics

Bimekizumab plasma concentrations will be summarized at each scheduled visit in AS0009 by treatment at completion of AS0008 and overall, using the SS.

If bimekizumab plasma concentration measurements are deemed to be BLQ, then for calculation of the derived statistics this sample result will be set to half the LLOQ. Descriptive statistics will be calculated only if at least 2/3 of the values are above the LLOQ at a given visit and $n \geq 3$. If this is not the case, only median, minimum, and maximum will be presented.

In addition, geometric mean bimekizumab plasma concentration (with 95% CI) time curves will be plotted versus time on linear and semi-logarithmic scales by treatment group at completion of AS0008.

The summary table for bimekizumab plasma concentrations will display n, geometric mean (and 95% CI), geometric CV%, arithmetic mean, SD, median, minimum, and maximum, where the geometric CV% is calculated using the following formula:

$$CV\% = \sqrt{e^{SD_{ln}^2} - 1} \times 100 \quad (13)$$

here SD_{ln} represents the standard deviation of the ln-transformed plasma concentration values.

Geometric mean plots will be repeated by cumulative ADAb positivity and treatment:

- The ADAb positive status will be considered in a cumulative manner at each time point:
 - A subject will be counted positive from the first time point at which the subject had a positive ADAb sample result regardless of any subsequent missing or negative ADAb sample results.
 - If a subject has only negative ADAb samples or only one missing sample with all negative ADAb samples up to a specific time point, the subject will be classified as negative at that time point. If the AS0008 Baseline sample is missing, then the sample will be classified as being negative for the cumulative ADAb status.
 - Thus, the number of subjects included in the geometric mean for positive and negative categories will vary by time point for each treatment.
- Two plots will be presented each displaying bimekizumab plasma concentration data in AS0009 only:
 - Considering cumulative ADAb in status in AS0009 only at each time point in AS0009
 - Considering cumulative ADAb status in AS0008 and AS0009 at each time point in AS0009

- Each plot (linear and semi-logarithmic) will be presented by treatment group at completion of AS0008 and ADA_b positive status (4 lines per plot)

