- Serious TEAEs by treatment group at completion of AS0008 and overall, by SS Sub-population.
- All TEAEs in AS0008 and AS0009 by treatment at time of AE onset (BKZ 160mg, BKZ 320mg and BKZ Total).
- Serious TEAEs in AS0008 and AS0009 by treatment at time of AE onset (BKZ 160mg, BKZ 320mg and BKZ Total).

- All TEAEs AS0008 and AS0009 by timing of onset relative to ADAb status in AS0008 and AS0009. This will include columns for the following:
 - TEAEs starting before the first ADAb positive result in AS0008 and AS0009 (includes ADAb Categories 2b only)
 - TEAEs starting on the same date or after the first ADAb positive result in AS0008 and AS0009 (includes ADAb Categories 2b, 3b, 4b, 5b and 6b)
 - TEAEs for subjects who are ADAb negative at all time points in AS0008 and AS0009 (includes ADAb Categories 1b only)

Note that any TEAEs occurring for a subject who was ADAb positive at AS0008 Baseline will therefore all occur after ADAb positivity; such subjects will be excluded from the first column in the above table. Subjects in Category 9b (missing) will not be included in the table.

The following categories of TEAE will be summarized by MedDRA SOC, HLT and PT, by treatment group at completion of AS0008 and overall:

- TEAEs leading to study discontinuation and/or permanent withdrawal of study medication.
- TEAEs leading to permanent withdrawal of study medication.
- TEAEs with a fatal outcome.
- All TEAEs by maximum relationship.
- Serious TEAEs by maximum relationship.
- TEAEs with a fatal outcome by maximum relationship.
- All TEAEs by maximum intensity.
- Non-serious TEAEs reported by more than the reporting threshold of 5% of subjects. The cut-off will be applied before rounding on each treatment group and overall.

A further summary will be presented by treatment group at completion of AS0008 and overall displaying the frequency of TEAEs by descending frequency of PT.

An additional table will be presented by MedDRA SOC, HLT and PT, by treatment at time of AE onset (BKZ 160mg, BKZ 320mg and BKZ Total) for all TEAEs in AS0009 and all TEAEs that were ongoing from AS0008 at the time of the AS0009 EV. Ongoing TEAEs are defined as TEAEs that started prior to the AS0009 EV and continued after the first dose of study medication in AS0009.

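### ADAb Category 9 (missing) does not require a missing sample, so every Category 1 (negative) subject also falls into it, and the TEAE-by-ADAb table both includes and excludes those subjects

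*SAP*

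**What the plan says.** SAP Section 9.2 sorts subjects into ADAb categories, each in an AS0009-only version (a) and a version combining AS0008 and AS0009 (b).

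- Category 1b (negative) "includes subjects who are negative at AS0008 Baseline and ADAb negative at all sampling points in AS0008 and AS0009 (including AS0009 SFU". Category 1a is the same for AS0009 alone.
- Category 2b (treatment-emergent positive) takes a negative or missing Baseline with a sample "positive at any sampling point post treatment in AS0008 and/or AS0009". A single positive is enough, whatever else is missing.
- Category 6b (inconclusive) takes a positive Baseline where "some AS0008 or AS0009 samples are missing, while other AS0008 and AS0009 samples are all ADAb negative".
- Category 9a (missing) takes a missing or negative Baseline where "all AS0009 samples are either missing or ADAb negative". For 9b the condition is that "all AS0008 or AS0009 samples are either missing or ADAb negative".

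Section 9.2 then asks for the number and percentage of subjects in each category.

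Section 10.2 plans a table of TEAEs by timing relative to ADAb status. Its negative column consists of Category 1b only. Its other columns draw on 2b, 3b, 4b, 5b and 6b. It adds: "Subjects in Category 9b (missing) will not be included in the table".

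Two other displays tolerate one gap. For the PK plots, Section 9.1 counts a subject as negative with "only one missing sample with all negative ADAb samples up to a specific time point". In Section 9.2, the figure of ASAS40 response over time by ADAb group calls a subject negative when one sample is missing or inconclusive and the rest are negative.

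**The concern.** A category meant for subjects who cannot be classified takes in the subjects with the most complete negative record. Two programmers following the text could produce different tables. One would apply Category 1 first; the other would flag every definition that is met and then drop 9b from the safety table, emptying its negative column. If all definitions are flagged, the category table no longer divides the Safety Set into separate groups.

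A smaller question sits behind this. Once the overlap is removed, the negative comparator in the TEAE table must have complete sampling in both studies, while subjects with gaps stay in the other columns (2b needs only one positive sample, and 6b is defined by missing samples). Gaps are to be expected: SAP Section 12.5 provides for visits not done, or held by telephone or video, because of COVID-19.

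**Working it through.** **Overlap.** The plan gives no figure to reproduce, so the check takes the definitions literally. With each sample negative, positive or missing, there are 3^k patterns over k post-Baseline samples. For a Baseline-negative subject, 2^k of them contain no positive sample.

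| Baseline-negative patterns | k = 4 | k = 8 |
|---|---|---|
| All negative: Categories 1 and 9 | 1 | 1 |
| No positive, at least one missing: Category 9 only | 16 − 1 = 15 | 256 − 1 = 255 |
| Any positive: Category 2 only | 81 − 16 = 65 | 6561 − 256 = 6305 |

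The all-negative pattern is the only double assignment across Baseline-negative, -positive and -missing subjects. Categories 4 and 5 were treated as one group, so the check says nothing about the boundary between them. One pattern has no category: a positive Baseline with every later sample missing. Category 6 does not collide with Category 3 because it requires missing samples.

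Adding a requirement for at least one missing sample to Category 9 takes the overlap from one pattern to none and moves no other pattern. Without it, if n1 subjects are in Category 1 and all N subjects have a category, the base categories sum to N + n1.

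**One missed sample.** Baseline negative, exactly one sample missing:

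- k = 4: 4 × 2^3 = 32 patterns. In 4 the rest are negative (Category 9); in 28 there is a positive (Category 2).
- k = 8: 8 × 2^7 = 1024 patterns. In 8 the rest are negative; in 1016 there is a positive.

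So a gap leads to Category 9 only when no sample is positive.

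**Possible size of the secondary point.** SAP Section 2.2.5 lists 13 AS0009 sampling points: EV, Weeks 12, 24, 36, 48, 72, 96, 120, 144, 168, 192 and 208, and SFU. The documents give no missed-sample rate p, so p is an assumption, as is independence between samples. Among Baseline-negative, never-positive subjects:

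- At least one gap: 1 − (1 − p)^13
- Two or more gaps: 1 − (1 − p)^13 − 13p(1 − p)^12

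| p | At least one gap | Two or more gaps |
|---|---|---|
| 1% | 1 − 0.878 = 12% | 0.7% |
| 2% | 1 − 0.769 = 23% | 2.7% |
| 3% | 33% | 5.6% |
| 5% | 1 − 0.513 = 49% | 13.5% |

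Category 9b, which governs the TEAE table, also counts AS0008 samples, so under the same assumptions its share would be larger.

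**The case against.** The best reply is that the intent is clear. Category 9 is headed as missing, and Section 10.2 names Category 1b as the negative column, under a description that openly requires negativity at all time points. A sensible programmer would apply Category 1 first and keep these subjects. A reader might infer that the overlap empties the negative column; on this workable reading it does not. The written contradiction remains, however, and the SAP gives no precedence rule to settle it.

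The reply is stronger on the secondary point. Requiring complete sampling before calling a subject negative is defensible, because a gap can hide a positive. The displays that tolerate one gap use different constructs. Section 9.1 is a cumulative status at each time point and counts a missing Baseline as negative. The ASAS40 figure leaves out SFU and needs two positive samples before a subject is positive. SAP Section 13.1.2 says the categories follow program conventions, so a change in one study could cost comparability. How many gaps to allow is therefore a judgement.

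The percentages are also only illustrative. Dropout and COVID-19 disruption cluster missed samples, and for a given average rate clustering lowers the share with at least one gap. It also weakens any reassurance from the two-or-more column. A subject who leaves after Week 48 has seven scheduled samples still to come before SFU. With one ET sample mapped forward under SAP Section 3.5 and an SFU sample, six are still lacking, if samples not taken after withdrawal count as missing.

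**Conclusion.** The definitions of Categories 9a and 9b are wrong as written. Every Category 1 subject also meets Category 9, the category table is not a partition, and the Section 10.2 table gives contradictory instructions for the same subjects. This rests on the text alone.

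Three stronger readings are not supported:

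- That any Baseline-negative subject with a missed sample becomes missing. With any positive sample the subject is Category 2.
- That the overlap by itself removes fully negative subjects from the TEAE table. The clear loss is of never-positive subjects with a missing Baseline or a gap, and it follows from Category 9 and the all-time-points column.
- That the denominator for ADAb incidence depends on attendance. SAP Section 3.1 bases percentages on the analysis set, and Section 9.2 uses the Safety Set unless stated otherwise. What depends on attendance is the split between Categories 1 and 9 and the size of the negative column.

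The 12% to 49% range holds only under assumed independent miss rates of 1% to 5%. The consequences are confined to descriptive ADAb displays; the primary TEAE and serious TEAE summaries use the full Safety Set.

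**What to change.** **Needed.** In Section 9.2, add to Categories 9a and 9b that at least one sample, at Baseline or later, is missing (for 9a, a later sample means one in AS0009). Wording that excludes subjects meeting Category 1 would also serve. State that Categories 1 to 6 and 9 are mutually exclusive, after checking the boundary between 4 and 5 and giving a home to the Baseline-positive subject with no later sample. The core change is one phrase in two definitions plus one sentence. It needs no new data and removes the contradiction in Section 10.2.

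**Optional.** Decide how the TEAE-by-ADAb table treats a Baseline-negative, never-positive subject with a single missed sample. Either of these would do:

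- Allow one missing sample in Category 1. This changes 1a, 1b, 9a and 9b and the column label in Section 10.2. It would still differ from Section 9.1 on a missing Baseline, and would treat a single gap more leniently than Category 6 does for Baseline-positive subjects.
- Keep the strict definition and add a sensitivity version of the table that includes these subjects. This costs one extra output and leaves the program's categories unchanged.

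In either case, say whether samples not taken after withdrawal count as missing.
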